#### 4.3.6.1. Lost to Follow-up

A participant will be considered lost to follow-up if:

- He/she fails to return for scheduled on-site or remote visits
- Randomisation and subsequent visits that cannot be done on-site, cannot be conducted remotely either
- Patient misses a clinic or remote visit and is unable to be contacted by the study centre.

The following actions must be taken if a participant fails to return to the clinic for a required study visit or cannot be contacted over the phone (or video/teleconference) to conduct a scheduled remote visit:

- The study centre must attempt to contact the participant's parents/carers and reschedule the missed visit as soon as possible and ascertain whether or not the participant wishes to and/or should continue in the study.
- Before a participant is deemed lost to follow-up, the Investigator or designee must make every effort to regain contact with the participant's parents/carers (at least

- 2 telephone calls and/or messages). These contact attempts should be documented in the participant's medical record.
- Should the participant's parents/carers continue to be unreachable, the participant will be considered to have withdrawn from the study.

# 4.3.7. Study Termination by the Sponsor

Kimberly-Clark reserves the right to discontinue the study overall or at any particular site at any time for the following reasons:

- Failure to meet enrolment goals overall or at any particular site
- Emergence of any efficacy/safety information that could significantly affect continuation of the study
- Violation of good clinical practice (GCP), the clinical investigation plan, or the contract by a site or Investigator, disturbing the appropriate conduct of the study

The Investigator/site will be reimbursed for reasonable expenses incurred in case of study termination.

# 4.3.8. Clinical Investigation Plan Deviations

The following events will be considered as the major violations of the clinical investigation plan and lead to the exclusion of the participant's data from the analysis:

- Absorbent pants/nappies (of any brand) used nocturnally in the 'no pants' group (up
  to 4 violations of the clinical investigational plan over the 4-week trial period will
  merit exclusion; these will be documented in the diary)
- No pants, or absorbent pants of a different brand, used nocturnally in the DryNites® group (up to 4 violations of the clinical investigation plan over the 4-week trial period will merit exclusion; these will be documented in the diary)
- Initiation of a prescribed therapy for NE (pharmacologic or bed alarm)

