#### 4.7.2. Direct-to-Patient Data Collection

The following data will be collected daily for all enrolled patients using an electronic diary from the morning following the baseline visit until discontinuation from the study:

- Were absorbent pants worn? Yes/No/Another brand
- Was the bed mat used? Yes/No/Another brand
- Did the child have an NE event? Yes/No
- How was the NE event managed? One response to be selected: Child slept through the night; child awoke but did not take any action; child awoke and changed pants/changed bed/visited toilet but did not disturb parents; child awoke and woke parents.

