### 5.3. Populations for Analyses

#### **Table 4 Analysis Sets**

Analysis Set	Description
Screened Set	All patients consented
Randomised Set	All patients in the Screened Set who are assigned to a randomisation group
Safety Analysis Set	All patients in the Randomised Set
Primary Analysis Set	All patients in the Randomised Set excluding participants with major violations of the clinical investigation plan
Extension Set	All patients in the Randomised Set who participate in the extension period

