6.4 Primary Analysis Set

The primary analysis set (PAS) will contain all patients in the Randomised Set excluding participants with major violations of the clinical investigation plan.

The following violation will be considered as major:

- Absorbent pants/nappies (of any brand) used nocturnally in the 'no pants' group (≥3 nights showing violation of the clinical investigational plan over the 4-week trial period will merit exclusion; these will be documented in the diary)
- No pants, or absorbent pants of a different brand, used nocturnally in the DryNites[®] group (≥3 night showing violation of the clinical investigation plan over the 4-week trial period will merit exclusion; these will be documented in the diary)
- Bed mat not used (≥3 nights showing violation of the clinical investigation plan over the 4week trial period will merit exclusion; these will be documented in the diary)
- Initiation of a prescribed therapy for NE (pharmacologic or bed alarm).

Document:	Y:\Kimberly-Clark\DryNites\Documentation\SAP\DryNites_SAP_v1.0_20200203		
Author:	[name] Version Number:		
		Version Date:	03Feb2020
Template No.: F	RWI_TP_BIOS0013 Revision 1		Reference: RWI_WI_BIOS0015

Effective Date: 15Jun2018

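### A DryNites-group child who becomes dry and then stops wearing pants is excluded from the Primary Analysis Set as a violator, which biases the primary difference against pants

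*Protocol*

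**What the plan says.** Protocol 4.3.8 defines the major violations that remove a child's data. For the continuing group the item is "No pants, or absorbent pants of a different brand, used nocturnally in the DryNites® group". For the discontinuing group it is "Absorbent pants/nappies (of any brand) used nocturnally in the 'no pants' group". SAP 6.4 carries the same pair of items. Neither document makes an exception for a child who no longer wets.

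The night counts differ. The protocol says "up to 4 violations of the clinical investigation plan over the 4-week trial period will merit exclusion"; the SAP says "≥3 night showing violation of the clinical investigation plan over the 4-week trial period will merit exclusion". The SAP also has a third item that applies to both groups, "Bed mat not used (≥3 nights showing violation of the clinical investigation plan". Protocol 4.3.8 does not have this item, and Protocol 4.1 and 4.4.2 make bed mats optional. The SAP states that it is based on version 1.0 of the plan; the protocol is version 3.0.

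Table 4 defines the PAS as "All patients in the Randomised Set excluding participants with major violations of the clinical investigation plan". The 95% equivalence interval is computed only on the PAS (Protocol 5.4.2, SAP 15.1.3). On the Randomised Set the diary data are summarised descriptively (Protocol 5.4.2, SAP 15). The only sensitivity analysis concerns missing data (SAP 15.1.4). The diary item behind the rule is "Were absorbent pants worn? Yes/No/Another brand" (Protocol 4.7.2), and it is recorded separately from whether the child wet.

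**The concern.** Absorbent pants are worn because the child wets. The protocol's own lay summary describes them as a help up to the point of full night-time dryness. A family whose child becomes dry on DryNites may well stop using them, and the exclusion then follows from the outcome the trial measures. In the no-pants group, a child who becomes dry and stays out of pants complies with the pants rule. That group's rule is triggered by putting pants back on, which is more plausible in a child who is still wet.

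The trial asks whether continued pants use delays dryness. A PAS that can lose resolved children from the continuing group makes that group look wetter than it was. If DryNites children truly resolved more often, the same mechanism could hide it.

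**Working it through.** **1. The plan's own figure.** Protocol 5.2 simulates Binomial(7, 0.95) against Binomial(7, 0.80), 15 vs 30 children, and states 99% power. Repeating this with a 95% Wald interval and margin 2/7 gives 97.8%, within two points. In that model a DryNites child has a fully dry week with probability 0.05^7, about 8 in 10 billion. The sample-size work therefore contains no resolved children and cannot show the effect of the rule.

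**2. Does the threshold protect the child?** A child off pants for all of Week 4 has 7 pants-free nights. That exceeds the SAP's 3 and every sensible reading of the protocol's count (any number from 1, at least 4, or more than 4). A child who stops only for the last one or two nights stays in under the SAP.

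**3. Bias with no true effect.** Assumptions, none of them given in the documents:
- a share r of each group is fully dry in Week 4
- the other children are wet on 95% of nights, so their mean is 7 × 0.95 = 6.65
- a share q of resolved DryNites children stop pants and are excluded
- 40 vs 80 children, that is, all 120 randomised 2:1

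No-pants mean: 6.65(1−r). DryNites mean in the PAS: 6.65(1−r)/(1−rq). Their difference is

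bias = 6.65 × (1−r) × rq/(1−rq).

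| r | q = 50% | q = 100% | DryNites children excluded (40 × r × q) |
|---|---|---|---|
| 2% | 6.65 × 0.98 × 0.01/0.99 = 0.066 | 6.65 × 0.02 = 0.133 | 0.4 to 0.8 |
| 5% | 6.65 × 0.95 × 0.025/0.975 = 0.162 | 6.65 × 0.05 = 0.333 | 1 to 2 |
| 10% | 6.65 × 0.90 × 0.05/0.95 = 0.315 | 6.65 × 0.10 = 0.665 | 2 to 4 |

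Units are nights per week, against a margin of 2 (SAP 15.1 explains 2/7 as two nights in a week). The bias does not depend on arm size.

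**4. Effect on the equivalence verdict (simulation, 40 vs 80).** SAP 15.1.3 names PROC TTEST but not the pooled or unequal-variance interval, so both are shown.
- *No true effect, r up to 10%.* Unequal-variance interval: equivalence is declared in at least 99% of trials with or without the exclusions. Pooled interval (others wet on 97% of nights), r = 10%, q = 100%: 99.5% without and 96.7% with.
- *No true effect, r = 20%, q = 100%.* The bias is 6.65 × 0.20 = 1.33 nights. Unequal-variance: about 93% falls to about 55%. Pooled (97%): 92.5% falls to 20.3%.
- *A mixture matched to 0.95/0.80.* DryNites: 5% fully dry and the rest always wet. No-pants: 10% fully dry and the rest wet on 0.80/0.90 = 0.889 of nights. The gap is 7 × 0.15 = 1.05 nights. With q = 100% it becomes 7 − 5.6 = 1.40. Unequal-variance: about 85% falls to about 71%, and at q = 50% to 78%.
- *The same rates with both groups all-or-none (5% vs 20% dry).* Unequal-variance: 66% falls to 45%. Pooled: 52% falls to 25%.

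**5. The opposite truth.** In a deliberately extreme case with 40% resolved on DryNites and 5% off pants (others wet on 97% of nights), the true difference is 0.97 × (0.60 − 0.95) = −0.34 as a proportion. Excluding all the resolved DryNites children turns it into 0.97 × (1 − 0.95) = +0.05. With the pooled interval, equivalence is then declared in 99.9% of trials instead of 1.4%.

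**The case against.** The best case against acting is that the event is rare. Children enter with at most about one dry night a month and a fully wet last run-in week. Protocol 1.2 calls resolution in this group low, and 5.4.6 calls it limited. Families in the DryNites group are assigned to continue, and a dry child who keeps wearing the pants stays in the PAS. At r = 2%, fewer than one child is expected to be lost. Diary results on the Randomised Set would let a reader see a shift, though without an interval. All of this stands and limits the size. It does not remove the mechanism.

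A reader might infer three stronger things that the documents do not support.
- **That the trial would often find against pants.** At r = 10% and q = 100%, the unequal-variance 95% interval excludes zero in 79% of simulated trials, against 4% without the exclusions. The plan does not decide on that. It asks whether the interval lies within the margin, and SAP 8.1 plans no confirmatory testing.
- **That the fall from 85% to 71% follows from the plan's assumptions.** Only the averages 0.95 and 0.80 are the plan's. The mixture is assumed, and under the plan's binomial model the rule would essentially never apply.
- **That resolved children can be lost from one group only.** This is true of the pants rule and of Protocol v3.0. Under SAP 6.4 as written, the bed-mat item could also remove a no-pants child who becomes dry and drops the mat.

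It is also fair to say that an exemption tied to dry nights is itself outcome-dependent and misses families who stop sooner. That is why it should not be the only remedy.

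**Conclusion.** The point holds in a limited form. As written, the pants rule can remove resolved children from the continuing group and never from the no-pants group, and it biases the PAS difference against pants. With no true effect and 2% to 10% resolved, the bias is roughly 0.07 to 0.67 nights a week, depending on how many families stop pants. The equivalence verdict hardly changes in that range: at least 99% with the unequal-variance interval, and about 97% at worst with the pooled one. It is materially affected only if resolution is commoner, around 20%, or if a true difference already takes up much of the margin. The rates of resolution and of stopping pants, the all-or-none form of resolution and the 40 vs 80 split are assumptions. The direction and the absence of an exemption come from the text. Separately, the protocol and SAP disagree on the night threshold and on bed mats, so the PAS is not uniquely defined.

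**What to change.** Change the analysis-set rule only; nothing that families are asked to do changes.

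1. In Protocol 4.3.8 and SAP 6.4, state that pants-free nights in the DryNites group do not count as violations once the child has recorded a pre-specified run of consecutive dry nights with DryNites worn. Seven is one example, mirroring the fully wet week required for randomisation.
2. Tabulate by arm the number excluded under each item, with their recorded wet nights.
3. Report the same 95% equivalence interval on the Randomised Set beside the PAS, because the exemption misses families who stop sooner. State which PROC TTEST interval is used.
4. Reconcile the night thresholds and the bed-mat item between SAP 6.4 and Protocol v3.0.

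The cost is a sentence in each document, one table and one repeated analysis. The diary already collects pants use and wetting nightly. The downside is that a few children stay in the PAS whose last nights were off pants after they had become dry.

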# 4.4. Study Treatment

#### 4.4.1. Medical Device

DryNites® pyjama pants are absorbent pants manufactured by Kimberly-Clark and designed to reduce the burden of bed-wetting. DryNites® are registered as Class I medical devices and CE marked; they are commercially available since 1995. They are not a treatment for NE and are not designed to cure NE.

DryNites® pyjama pants are available for male and female children in 3 sizes (for children aged 3-5, 4-7 and 8-15 years). It is expected that the 4-7- and 8-15-years sizes will be used in this study.

DryNites® Medical Device Incidents, including those resulting from malfunctions of the device, must be detected, documented, and reported by the Investigator throughout the study (see Section 4.6.4).

# **4.4.2.** Provision of Study Treatment

DryNites®, defined as the study treatment, is commercially available medical device of Class I and will be provided free of charge to the study participants. DryNites® should be used in accordance to this clinical investigation plan instructions. Study treatment and absorbent bed mats will be supplied to the participants by the Investigator/site; however, the use of bed mats is optional. A 4-week supply will be distributed to each participant's parents/carers at each visit Day 0, Day  $28 \pm 7$  days, and Day  $56 \pm 7$  days. In case of remote visits, study materials will be shipped by the site to the patient's address according to local law and regulatory instructions. All packages will be labelled "for use in clinical investigation only" (in the applicable local languages).

The younger age group will be provided with the 4–7 years DryNites® size. Parents/carers in the older age group will select whether age 4–7 or age 8–15 DryNites® size is most appropriate. DryNites® age 4–7 years are provided in packs of 10. As such, each participant will be provided with 4 packs of DryNites® to cover each 4-week period.

DryNites® age 8–15 years are provided in packs of 13. As such, each participant will be provided with 3 packs of DryNites® to cover each 4-week period.

Absorbent bed mats are provided in packs of 12. Each participant randomised in the intervention group (discontinuation of DryNites® pants) will be provided with 3 packs of bed mats to cover each 4-week period. Participants randomised in the control group (continuation of DryNites® pants) will receive 1 pack of bed mats per 4-week period. The use of bed mats is optional.

Any surplus of DryNites® and absorbent bed mats at the end of each 4-week period can be kept by the participant.

# 4.4.3. Storage/Accountability of DryNites® and Absorbent Bed Mats

All participating centres will be provided with multiple DryNites® sizes for distribution, based on their anticipated enrolment.

Only participants enrolled in the study may receive study treatment and only authorised study centre staff may supply or administer study treatment. All study treatments must be stored in a secure and monitored (manual or automated) area with limited access to the Investigator and authorised study centre staff.

The Investigator, a member of the study centre staffs, or a hospital pharmacist must maintain an adequate record of the receipt and distribution of all DryNites® and bed mats supplies using the Device Accountability Form. These forms must be available for inspection at any time.

At the end of the study, all unused materials will be returned by the site to Kimberly-Clark.

# 4.4.4. Concomitant Therapy

Concomitant therapies not intended to treat NE can be provided as standard of care during the conduct of this study.

#### 4.5. Outcome Definitions and Measures

# 4.5.1. Primary Outcome Measure

Every morning, starting from the date of parent(s)/carer(s) written informed consent through discontinuation of the study, the parent/carer of the participant will complete an electronic diary to record events from the previous night, including the following details:

- Were absorbent pants worn?
- Was the bed mat used?
- Did the child have an NE event?
- How was the NE event managed? (1 response to be selected: Child slept through the night; child awoke, but did not take any action; child awoke and changed pants/changed bed/visited toilet, but did not disturb parents; child awoke and woke parents)

Please refer to Section 4.7.2 for details.

For both the older and younger participant populations, the primary endpoint will be the average number of wet nights in Week 4/last week of the intervention period.

A clinically significant reduction in NE is considered a reduction of  $\geq 2.0$  wet nights per week.

# 4.5.2. Secondary Outcomes

Quality of Life and sleep quality will be assessed via a set of validated questionnaires for the participants and their parent/carers at each study visit (Day 0, Day  $28 \pm 7$ , Day  $56 \pm 7$  and Day  $84 \pm 7$  [optional]) or remotely in case of remote visits including baseline. Additionally, the perception of DryNites® attributes, compared to previously used absorbent products will be evaluated through 2 specific questionnaires designed for this study.

Questionnaires will be provided in electronic format and can be administered on-site via hand-held devices or computers or completed remotely via the parent/carer's own device.

As a contingency to restrictions related to the outbreak of Covid-19, the baseline, randomisation, and any subsequent visits could be performed remotely via phone or video/teleconference, if an on-site visit cannot be performed. For remote visits, PRO questionnaires will be accessed through the parent's/carer's own electronic device. The PRO questionnaires will be available after a given visit (and should be completed before the next visit). The PRO questionnaires can also be completed remotely, within the same time window, if completion is not feasible during any on-site visit including baseline.

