#### Data collection/Data Sources:

Participants will be assessed on Day 0 (baseline), for demographics, height and weight, medical history, concomitant medication, prior use of absorbent pants/nappies, and full physical examination (optional). In case of remote visit, height and weight and full physical examination will be done when the visit is performed on-site. At Day 28 ± 7days (end of run-in and randomisation), Day 56 ± 7days (end of intervention/core trial period) and Day 84 ± 7 days (end of extension period), participants will be assessed for adverse events (AEs) since the previous visit, concomitant medication used to treat AEs, and patient-reported outcome (PRO) questionnaires. Baseline, randomisation, and any subsequent visit could be performed remotely via phone or video/teleconference, if an on-site visit cannot be performed. For remote visits, PRO questionnaires will be accessed through the parent's/carer's own electronic device and study materials (i.e., DryNites®, bed mats) will be shipped to the patient. The PRO questionnaires will be available after a given visit (and should be completed before the next visit). The PRO questionnaires can also be completed remotely, within the same time window, if completion is not feasible during any on-site visit including baseline. Dry and wet nights will be captured every day from the start of the run-in period to discontinuation of the study through an electronic diary, accessible through the parent's/carer's own device (smart phone, tablet, or computer).

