Study specific mandated clinic visits will be required as part of the participation in this study. Baseline, randomisation, and any subsequent visit (i.e., Visit 3 and 4) can also be performed remotely in case the patient cannot visit the site in person. Participants will be assessed on Day 0 (baseline), Day  $28 \pm 7$ days (end of run-in and randomisation), Day  $56 \pm 7$ days (end of intervention/core trial period), and Day  $84 \pm 7$ days (end of extension period).

Participants will be reimbursed for their travel expenses, where applicable.

[figure not shown]
Dry and wet nights will be captured every day from the start of the run-in period to discontinuation of the study through an electronic diary, accessible through the parent's/carer's own device (smart phone, tablet, or computer).

Quality of life (QoL) and sleep questionnaires will be completed by children and parents/carers in electronic format on-site during the clinic visit, using site-based hand-held devices (e.g., tablets) or computers, from randomisation onwards. In case the questionnaires are not completed during the clinic visit or if a visit is performed remotely, the questionnaires will be accessible through the parent's/carer's own device. Questionnaires will be accessible after the visit and should be completed as close to the visit as possible (and before the next visit).

The perception of the absorbent products will be assessed by 2 questionnaires, at study entry (on previous absorbent products) and at the end of the run-in period (on DryNites®, compared to the previously used absorbent pants/nappies).

An overview of the trial design is provided in Figure 1.

Figure 1 Study Design

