# 4.3.5. Methods for Assigning Patients to Treatment Groups

A patient randomisation list will be produced using permuted block randomisation stratified by age group (4–<6 years old and  $\ge6-8$  years old) and a 2:1 group allocation for discontinuation or continuation of the use of DryNites® pyjama pants.

When a patient is qualified for entry into the randomised treatment period, treatment assignment will be performed by means of an IWRS on a central level on Visit 2 (Day  $28 \pm 7$  days).

Before the study is initiated, the log in information and directions for the IWRS will be provided to each study centre.

The Investigator or his/her delegate (study coordinator) will log on to the EDC and confirm that the patient fulfils the eligibility criteria and proceed with the randomisation. Participants will be assigned a unique number (randomisation number) in ascending numerical order on the next available record in the group at each study centre. The randomisation number encodes the participant's assignment to 1 of the 2 arms of the study (No Pants arm or DryNites® arm).

The treatment assignment (Discontinuation vs. continuation of DryNites®) will be captured in the EDC from the IWRS.

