#### **5.4.2.** Planned Analyses

The total number of patients included in each analysis set along with the number of patients for each of following categories will be provided as disposition analysis:

- Patients consented, overall and by age group  $(4-<6 \text{ years and } \ge 6-8 \text{ years})$
- Patients randomised, overall and by age group  $(4-<6 \text{ years and } \ge 6-8 \text{ years})$
- Patients who completed the 4-week intervention period, overall and by age group  $(4-<6 \text{ years and } \ge 6-8 \text{ years})$
- Patients who entered the extension period, overall and by age group (4–<6 years and  $\ge$ 6–8 years)
- Patients who completed the extension period, overall and by age group (4-<6 years) and  $\ge 6-8 \text{ years})$
- Time and reasons for discontinuation of the study, overall and by age group  $(4-<6 \text{ years and } \ge 6-8 \text{ years}).$

For all categories except the Screened Set, the percentages will be calculated using the number of randomised patients as the denominator for each treatment group.

Baseline will be defined as the data collected at or prior to randomisation; demographic and baseline characteristics, disease history, physical examination, medical history and concomitant medication will be summarised with appropriate descriptive statistics by group and separately for age subgroups.

These summaries will be provided for the Screened and Randomised Sets.

Body height, body weight and BMI will be summarised. The calculated BMI will be classified as follows based on comparison with:

- Underweight (<5th percentile for sex and age),
- Normal (from 5th to less than 85th percentile for sex and age),
- Overweight (from 85th to less than the 95th percentile for sex and age),
- Obese ( $\geq 95^{th}$  percentile for sex and age).

Physical examination will be summarised as percentage of patients with normal/abnormal result overall and as per the physical examination features listed in Section 4.5.3.2.

Pathologies associated with past medical or surgical history will be summarised by primary SOC and PT as per MedDRA. Concomitant therapies will be summarised by Anatomical Therapeutic Chemical (ATC) Classification System.

Direct- to-patient data will be analysed descriptively at each assessment along with applicable change from baseline on the Randomised Analysis Set and Primary Analysis Set.

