7.1 Reference Start Date

Reference start date is defined as the day of the randomisation and will appear in every listing where an assessment date or event date appears.

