7.2 Baseline

Baseline is defined as the last non-missing measurement taken prior to reference start date (including unscheduled assessments). In the case where the last non-missing measurement and the reference start date coincide, that measurement will be considered pre-baseline, but AEs and medications commencing on the reference start date will be considered post-baseline.

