7.3 Windowing Conventions

The following table describes assignment of visit windows to the following data for purposes of analysis:

Table A:Windowing

Assigned Study Day (Inclusive)		Visit Assigned	
From	То		
-35	0	Visit 1	
1	1	Visit 2	
2	42	Visit 3	

Template No.: RWI_TP_BIOS0013 Revision 1

Reference: RWI_WI_BIOS0015

Effective Date: 15Jun2018

43 63 Visit 4

To define cut on visits to the patient's diary, visit date will be used as reference along with windowing conventions.

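### No section puts the Visit 2 quality-of-life and sleep forms before the open-label allocation, so a form completed after the visit may be too late to be the baseline or be filled in with the arm known

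*Protocol*

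**What the plan says.** **Allocation.** The trial is open-label (protocol 4.1). Protocol 4.3.5 states that "treatment assignment will be performed by means of an IWRS on a central level on Visit 2".

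**Timing of the forms.** On-site completion at the visit is the default (protocol 4.1). The synopsis (Data collection) allows remote visits: "Baseline, randomisation, and any subsequent visit could be performed remotely via phone or video/teleconference, if an on-site visit cannot be performed". For a remote visit, or a form not completed on site, protocol 4.1 says "Questionnaires will be accessible after the visit and should be completed as close to the visit as possible (and before the next visit", and protocol 4.5.2 says "The PRO questionnaires will be available after a given visit (and should be completed before the next visit".

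**Who completes them at Visit 2.** Protocol 4.7.3 restricts the forms to randomised participants. Table 2 footnote (f) refers to participants who meet the randomisation criterion. Neither gives an order relative to allocation.

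**What counts as baseline.** Protocol 5.4.2: "Baseline will be defined as the data collected at or prior to randomisation". SAP 7.1: "Reference start date is defined as the day of the randomisation". SAP 7.2 takes the last non-missing value before that date and adds: "In the case where the last non-missing measurement and the reference start date coincide, that measurement will be considered pre-baseline".

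**How it is used.** SAP 8.2 and 15.2.3.1 make the baseline score the ANCOVA covariate and the reference for change from baseline.

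**The concern.** A baseline covariate should be measured before the arm can influence it. Here a family with a remote Visit 2 that follows the protocol exactly completes the form after allocation. On a later day, the form falls outside both baseline definitions. On the same day, it may reflect a reaction to the known arm.

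In the first case the child can drop out of the ANCOVA and the change-from-baseline summaries. Because that loss arises after an open-label allocation, it can differ by arm. In the second case part of the reaction enters the covariate and shifts the adjusted comparison. The problem touches four of the five secondary objectives. The diary-based primary endpoint and the fifth secondary objective, on product perception, do not use this baseline.

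**Working it through.** The plan states no figure to reproduce here. The check takes the timing rules in order, then sizes the consequences under stated assumptions.

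**Step 1: how long the form is open.** Visit 2 is Day 28 ± 7 and Visit 3 is Day 56 ± 7 (protocol 4.1).
- Shortest: 49 − 35 = 14 days
- Nominal: 56 − 28 = 28 days
- Longest: 63 − 21 = 42 days

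Counting from the randomisation day to the day before Visit 3, only the first of these 14, 28 or 42 days can satisfy SAP 7.1–7.2. The other 13, 27 or 41 cannot.

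**Step 2: is there an earlier form to fall back on?** If a Day 0 form exists, SAP 7.2 would use it automatically.
- For: protocol 4.5.2 lists Day 0. The synopsis mentions remote completion at any on-site visit including baseline. SAP 15.2 speaks of each clinic visit.
- Against: the QoL/sleep row in Table 2 starts at Visit 2, the Visit 1 list in protocol 4.7.1 omits all four questionnaires, and the synopsis and protocol 4.1 start them from randomisation.

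The documents do not settle this.

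**Step 3: do the missing-data rules help?** Protocol 5.4.5 and SAP 8.3 permit imputation but do not require it. The model that SAP 8.3 points to (SAP 15.1.2) contains no questionnaire score. SAP 15.2.2 handles missing items by prorating, not a whole missing form.

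**Step 4: size if late forms leave no baseline.** Assumptions: no Day 0 form; baseline–outcome correlation 0.6, so the residual SD is √(1 − 0.36) = 0.8; share lost f = 10, 30 or 50%, proportional across arms. The number randomised is either 80 vs 40 (protocol 4.3 aims to randomise about 120) or 60 vs 30 (protocol 5.2 needs 45 per age group at randomisation, and 2 × 45 = 90).

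The standard error rises by 1/√(1 − f) = 1.054, 1.195 or 1.414. The half-width of the 95% CI is t × 0.8 × √(1/n₁ + 1/n₀), in SD units:

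| Lost | 80 vs 40 at start | 60 vs 30 at start |
|---|---|---|
| 0% | 0.307 (80/40) | 0.356 (60/30) |
| 10% | 0.324 (72/36) | 0.375 (54/27) |
| 30% | 0.368 (56/28) | 0.428 (42/21) |
| 50% | 0.439 (40/20) | 0.511 (30/15) |

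If 12 of 120 are lost from one arm only, the ratios are:
- continuation arm: √(1/80 + 1/28) / √(1/80 + 1/40) = 1.134
- discontinuation arm: √(1/68 + 1/40) / √(1/80 + 1/40) = 1.029

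**Step 5: size if same-day forms are completed with the arm known.** The ANCOVA bias is −(correlation) × (between-arm shift in the covariate). With an assumed reaction of 0.2 SD in 10, 30 or 50% of children, its magnitude is 0.6 × share × 0.2 = 0.012, 0.036 or 0.060 SD. The direction depends on the reaction. If every child in an arm shifted by 0.1–0.3 SD, with correlation 0.3–0.7, the product runs from 0.3 × 0.1 = 0.03 to 0.7 × 0.3 = 0.21 SD.

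**Step 6: keep or discard such same-day forms?** With 80 vs 40, the full-data standard error is 0.8 × √(1/80 + 1/40) = 0.155. Keeping the forms gives a root mean squared error of √(0.155² + bias²) = 0.155, 0.159 or 0.166. Discarding them gives a standard error of 0.163, 0.185 or 0.219. Keeping them is better at each assumed share.

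**The case against.** The strongest reply is that the exposure is small. On-site completion is the default, remote visits are a Covid-19 contingency, and protocol 4.1 asks for completion close to the visit. SAP 8.1 plans no confirmatory testing, and SAP 15.2.3.1 calls the questionnaire p-values purely exploratory. CIS asks about the past two weeks, so an immediate reaction to the arm should be limited there. The SAP is based on plan version 1.0, so part of the mismatch may be version lag. Footnote (f) of Table 2 would allow completion before allocation.

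All of this limits the size and stands. It does not remove the gap: footnote (f) permits the right order without requiring it, and the after-visit rule prevents it for remote visits.

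A reader might infer more than the documents support:
- **That every late form removes a child from the ANCOVA.** This depends on the unresolved Day 0 form.
- **That SAP 7.2 plainly accepts a same-day form as baseline.** That is the likely intent, since there is no time check, but the term pre-baseline is ambiguous.
- **That late forms will be analysed as Visit 3 values.** Table A in SAP 7.3 assigns Days 2–42 to Visit 3, but its introduction, "The following table describes assignment of visit windows to the following data for purposes of analysis", never names the data. The only application stated is the diary.
- **That late baselines dilute the effect.** This would require keeping them by visit label, against both baseline definitions.
- **That all forms completed after allocation should be discarded.** Step 6 shows this costs more than it saves for same-day forms, and it adds a loss that may depend on arm.

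**Conclusion.** The concern holds in this form. The plan does not secure a pre-allocation baseline for the four questionnaire endpoints, and its own after-visit rule produces a form that is either too late to be the baseline or possibly completed with the arm known. Loss of the child's baseline is conditional on there being no Day 0 form.

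The effect is probably modest. Under the assumptions in steps 4 and 5, the standard error rises by about 5–41%, or the estimate moves by about 0.01–0.06 SD. The 0.21 SD figure needs a reaction across a whole arm and is an upper illustration. The late rate, the correlation and the reaction come from no section of the documents, and the starting numbers depend on whether 80 vs 40 or 60 vs 30 are randomised. The sponsor should correct this; it does not threaten the primary analysis.

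**What to change.** 1. **Protocol synopsis, 4.1, 4.5.2, 4.7.3 and Table 2.** Open and complete the Visit 2 QoL/sleep forms, on site or on the family's device, after the criterion of seven wet nights in the last run-in week is confirmed and before the IWRS allocation is made and disclosed. Align 4.7.3 with Table 2 footnote (f), since the forms would then precede randomisation.
2. **Day 0.** Reconcile protocol 4.5.2 with Table 2 and 4.7.1 on whether these forms are also given at baseline.
3. **SAP 7.2 and 7.3.** Replace the term pre-baseline with clear wording. Assign questionnaires by nominal visit. Never use a Visit 2 form dated after the randomisation day as a baseline or as a Visit 3 value; use a valid Day 0 form if one exists.
4. **Children already randomised.** Keep same-day forms as baseline in the main ANCOVA. Report by arm how many forms were late or time-stamped after allocation. Exclude those time-stamped after allocation only in a sensitivity analysis.

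The cost is a site instruction, a change in the release order of the electronic forms, and SAP wording; no new data are needed. Forms and allocation are both captured in the EDC (protocol 4.3.5 and 6.1), so their order can be checked if both carry a time stamp, which is assumed. The downside is that some remote randomisations wait until the forms are submitted.
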